### ***Rationale for Placebo in Full Enrollment Cohort***

Placebo, rather than a benefit licensed vaccine, will be used for comparison to vaccine to allow safety comparisons between vaccine and placebo as currently emergency use authorized COVID-19 vaccines are not widely available. The number in the placebo group have been decreased to expose fewer participants to placebo. The inclusion of placebo group will also maintain the blind, allowing the unbiased evaluation of safety, immunogenicity, and clinical outcomes related to COVID-19-like illness and SARS-CoV-2 infection by treatment group.

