After the planned preliminary interim of the Sentinel Cohort participants, a decision to discontinue the development of the mRNA COVID-19 vaccine was made. On September 27, 2021, all Investigators were informed to terminate further vaccinations and enrollment. All enrolled participants were to be unblinded to allow them to make their decision to receive an authorized COVID-19 vaccine. All clinical sites were to contact participants to inform them of the discontinuation of further study vaccinations, told what intervention they received and invited to come in for an unscheduled visit for counseling to answer any questions about the study, to discuss available options for receipt of an approved /authorized COVID vaccination, and were requested to provide unscheduled blood draw for serological assessment (UBXX). Participants were informed that additional D22 or D36 blood draws for serological assessment would be appreciated but are not mandatory. No protocol defined schedule visits or blood draws at timepoints later than D36 were required. Monitoring for SAEs, AESIs, medically attended AEs, and pregnancy and collection of influenza and COVID-19 vaccines were continued with safety calls. On March 15, 2022, after concurrence from regulatory authorities, Investigators were notified of the decision to end the study at the 6-month safety follow-up instead of 12-month follow-up.

This version 5.0 of SAP is updated for the final unblinded analysis. The sections of Trial Objectives and Trial Design and Plan are kept the same with the final protocol, but modifications are made in Section 4 and Section 5 for endpoint derivation, statistical methods, and populations used in analyses, to reflect the changes needed for the final analyses.

2 Trial Objectives

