4.4.1.5.8 MAAE

A MAAE is a new onset or a worsening of a condition that prompts the participant to seek unplanned medical advice at a physician’s office or Emergency Department. Physician contact made over the phone or by e-mail will be considered a physician office visit for the purpose of MAAE collection. This includes medical advice seeking during the study visit or routine medical care. This definition excludes pediatric check-ups, follow-up visits of chronic conditions with an onset prior to entry in the study and solicited reactions.

MAAEs will be analyzed during the following time periods:

- Within 21 days after each injection
- During the study (ie, all MAAEs occurred during entire the study or the cutoff date which corresponds to the date of any interim analysis)

Note: MAAEs with date of onset before first vaccination (negative time of onset) will not be included in analysis but will be listed separately.

Main safety analysis will include only those MAAEs with time of onset before a participant received a non-study authorized/approved COVID-19 vaccine, if applicable. MAAEs with time of onset on or after the date of receiving a non-study authorized/approved COVID-19 vaccine will be listed separately.

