5.1 Statistical Methods

Safety, immunogenicity, and efficacy analysis will be undertaken including those data collected before the date of receiving an authorized/approved COVID-19 vaccine. Those data collected on or after receiving an authorized/approved COVID-19 vaccine will be listed separately.

For those participants who did not receive an authorized/approved COVID-19 vaccine outside the study, immunogenicity data collected until the last scheduled/unscheduled study visit will be used for analysis. Rules about how to handle unscheduled visit are detailed in Table 5.2. Safety data collected until the last phone contact will be used for analysis if participants did not receive an authorized/approved COVID-19 vaccine outside the study

Safety analyses will be conducted based on two populations: *i*) participants in the Full Enrollment Cohort (Cohort 1 and 2) only, and *ii*) all participants in the Full Enrollment Cohort and Sentinel Cohort, if necessary. Immunogenicity analyses and efficacy analyses will be conducted based on the combined population (Full Enrollment Cohort + Sentinel Cohort) only, in which the same

dose-level group in Sentinel Cohort and Full Enrollment Cohort will be pooled. Subgroup analyses will be performed by age-group.

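### The SAP cuts safety and COVID-19 case data only at an outside vaccine, so the long-window tables and the harm test mix blinded with open-label reporting in the Full Enrollment Cohort

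*SAP*

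**What the plan says.** SAP Section 1, repeated in Section 5.7, describes the stop: "On September 27, 2021, all Investigators were informed to terminate further vaccinations and enrollment". It continues: "All enrolled participants were to be unblinded to allow them to make their decision to receive an authorized COVID-19 vaccine". Sites were to contact participants, tell them what they had received and invite them to a counselling visit. Data collection did not end there: "Monitoring for SAEs, AESIs, medically attended AEs, and pregnancy and collection of influenza and COVID-19 vaccines were continued with safety calls". Investigators were notified on 15 March 2022 of the "decision to end the study at the 6-month safety follow-up instead of 12-month follow-up".

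SAP 5.1 sets the data cut: "Safety, immunogenicity, and efficacy analysis will be undertaken including those data collected before the date of receiving an authorized/approved COVID-19 vaccine". For participants without such a vaccine, "Safety data collected until the last phone contact will be used for analysis if participants did not receive an" outside COVID-19 vaccine. SAP 4.4.1 limits the cut to selected safety endpoints, and the SAE, AESI and MAAE subsections each repeat it.

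SAP 5.1.1.2 tabulates SAEs, AESIs and MAAEs within 21 days of injection and over the entire study, by intervention group. It also plans a harm analysis on the Safety Analysis Set at the final analysis. This is a one-sided conditional exact binomial test at 0.05 of how COVID-19 cases split between pooled vaccine and pooled placebo.

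Protocol 4.2 gives the purpose of the control arm: "The inclusion of placebo group will also maintain the blind, allowing the unbiased evaluation of safety, immunogenicity, and clinical outcomes". Protocol 6.3.2 intended participants and investigators to stay blinded individually for the duration of the study, apart from safety needs.

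**The concern.** Version 5.0 of the SAP was written for the final analysis of a stopped study, and it revised Sections 4 and 5 for that purpose. Individual unblinding changes how outcomes get reported, yet neither section has a rule for it.

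Several outcomes depend on someone who may know the arm. An MAAE begins with a participant seeking advice, and relatedness of unsolicited systemic events is judged by the investigator. COVID-19-like illness is found when a participant reports symptoms, by passive contact or surveillance call. A person told that they received a discontinued vaccine and a person told that they received saline may differ in what they report and whether they seek testing.

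At stake is whether the vaccine and placebo columns of the whole-study tables, and the case split in the harm test, can be read as the blinded comparison that the protocol describes. Person-time denominators would not remove this problem, because it concerns which events are captured rather than how long people are followed.

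**Working it through.** **1. Is there a cut at unblinding anywhere in the SAP?**

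- Sections 4.4.1, 4.4.1.3 (SAEs), 4.4.1.5.7 (AESIs) and 4.4.1.5.8 (MAAEs): the cut is the date of an outside vaccine.
- Section 5.1: same cut; otherwise last phone contact.
- Section 5.1.1.2, harm analysis: pooled vaccine against pooled placebo, with no unblinding rule.
- Section 5.1.2.2: mentions unblinding only to describe when unscheduled serology samples were drawn.
- Section 5.7: says that the final analysis is conducted unblinded, which describes the analysis and not a data cut. Its list of changes adds no split.

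So no rule separates onset before from onset after unblinding.

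**2. Which outputs are affected?** The Sentinel Cohort was open-label from the start, so the point concerns the Full Enrollment Cohort. The whole-study SAE, AESI and MAAE tables and the COVID-19 cases span unblinding for anyone followed past it. The solicited (7-day) and unsolicited (21-day) tables are affected only if the time from injection to being told is at most 7 or 21 days. The documents give no individual dates; 27 September 2021 is the earliest possible one.

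**3. What share of follow-up is open-label?** The plan states no figure, so this is illustrative. Assume 180 days of follow-up after the last injection, no outside vaccine, and last injection *d* days before unblinding. The open-label share is (180 − *d*)/180.

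| *d* (assumed) | Open-label share |
|---|---|
| 14 | 166/180 = 92% |
| 30 | 150/180 = 83% |
| 90 | 90/180 = 50% |
| 150 | 30/180 = 17% |

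An outside vaccine after unblinding lowers the share, because analyzed follow-up ends there. Calls continuing beyond 180 days would raise it.

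**4. How sensitive is the harm test?** Inputs are the planned Full Enrollment numbers in Protocol Table 4.3: vaccine 6 × 44 = 264, placebo 2 × 22 = 44, total 308, which reproduces the plan's 308. The null vaccine share is 264/308 = 0.857.

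- Smallest number of cases that can reject: 0.857^19 = 0.053, above 0.05; 0.857^20 = 0.0458, below it. At 20 cases, all 20 must be in the vaccine arms.
- Suppose there is no true harm, but over the whole follow-up cases are captured *r* times as often per vaccine recipient as per placebo recipient (*r* is assumed). The vaccine share becomes 264*r*/(264*r* + 44), and the chance of rejecting at 20 cases is that share to the power 20.

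| *r* | Vaccine share | Chance of rejecting at 20 cases |
|---|---|---|
| 0.5 | 0.750 | 0.003 |
| 0.8 | 0.828 | 0.023 |
| 1 | 0.857 | 0.046 |
| 1.25 | 0.882 | 0.082 |
| 1.5 | 0.900 | 0.122 |
| 2 | 0.923 | 0.202 |

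If only part of follow-up is open-label, the overall *r* lies closer to 1 than the open-label *r*. Actual enrollment and case counts are not in the documents.

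**The case against.** **The unblinding is disclosed, and little formal comparison remains.** This is true. Efficacy, correlates and aggregated-group analyses were dropped (SAP 5.1.2.4 and 5.7), the other tables are descriptive, and the harm test cannot reject below 20 cases at the planned allocation. That limits the weight of the point. It does not make the two kinds of reporting separable in the tables that remain.

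**The 21-day tables already provide a partial separation.** They do for early events. They do not help with MAAEs, AESIs or COVID-19 cases with later onset.

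**Cases need laboratory confirmation.** A positive NAAT or nucleoprotein serology is required, and serology does not depend on symptom reporting. But the swab usually follows a symptom report, and after the stop no scheduled draws later than D36 were required, so serological detection also came to rest on who attended.

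**Counselling visits do not inflate MAAEs by themselves.** Because the definition says "This includes medical advice seeking during the study visit or routine medical care", a reader might infer that every counselling visit counts. It does not: the same definition first requires a new or worsening condition that prompts unplanned advice. No exclusion rule is needed.

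**Restricting the harm test costs sensitivity.** This stands. A test that already needs 20 of 20 cases should not lose cases in its main form.

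**The separate tables, listings and figures document might flag unblinding.** It was not available. The data-cut rules nonetheless sit in SAP 4.4.1 and 5.1, which are silent.

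**Conclusion.** The point holds for the Full Enrollment Cohort's whole-study SAE, AESI and MAAE tables, the COVID-19 case counts and the harm test. Followed as written, the SAP puts blinded and open-label reporting in the same cells. The change should be made because it is cheap and drops no event.

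The size is uncertain. The open-label share runs from about 92% to 17% under the assumed dates, 180-day follow-up and no outside vaccine. The harm-test illustration shows that moderate differential capture could move the rejection rate well above or below its nominal level, but the capture ratios are assumed and the direction is unknown.

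Three stronger readings are not supported. A reader might infer that all safety tables are compromised; the solicited and 21-day tables are touched only for participants told inside those windows, and solicited and injection-site reactions are related by convention. A reader might take 27 September 2021 as everyone's unblinding date; it is the date on which investigators were informed. A reader might conclude that most follow-up was open-label; the documents give neither vaccination nor unblinding dates, so no such figure can be stated.

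**What to change.** In SAP 4.4.1 and 5.1, add each participant's unblinding date as an analysis variable. For the Full Enrollment Cohort, show the whole-study SAE, AESI and MAAE tables and the COVID-19 case counts by intervention group in two columns, and keep the overall total:

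- onset before unblinding;
- onset from unblinding to outside vaccine or last contact, labelled open-label.

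In SAP 5.1.1.2, keep the harm test on all cases as planned and add a sensitivity version restricted to onset before unblinding. State beforehand that the restricted version has low sensitivity.

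The cost is one date variable, one added column and one extra run of the test. The documents do not say whether the date was captured for this unblinding; if it was not, it would have to come from site contact records. The downside is small counts in the blinded column.

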**Overall Design**

Type of design	Phase I/II, first-in-human, multi-center, safety and immunogenicity study comprised of 2 sequential cohorts: 
 
Lead-in, open-label, Sentinel Cohort (initial target of 25 participants), with Complete Sentinel Early Safety Data Reviews (CS-ESDRs)
 
 
In case an alert threshold is met in a dose-level group, the Sentinel Cohort for the corresponding dose-level group could be expanded to reach a total of approximately 25 participants
 
 
Randomized, modified double-blind, placebo-controlled Full Enrollment Cohort (initial target of 308 participants, but actual number could be lower as it will be determined by dose-levels progressing after CS-ESDR). Includes Cohort 1 and Cohort 2.
 

Phase	I/II
Control method	
 
Open-label, without placebo group for Sentinel Cohort
 
Placebo-controlled for Full Enrollment Cohort
 

Study population	Healthy, adults 18 years of age and older without prior serologic evidence of SARS-CoV-2 infection
Countries	United States, Honduras
Level and method of blinding	
For Sentinel Cohort
 
 
Open-label without blinding of participants, site Investigators and staff, and Sponsor
 
No blinding for injection schedule as all participants will receive 2 vaccinations
 
 
For Full Enrollment Cohort
 
 
Blinding for study intervention assignment (formulation): participants, outcome assessors, Investigators, laboratory personnel, Sponsor study staff
 
No blinding for injection schedule
 
Only study site staff who prepare and administer the vaccine and are not involved with the safety evaluations will be unblinded to study intervention assignment
 

Study intervention assignment method	Sentinel Cohort: sequentially assigned study intervention; Full Enrollment Cohort: randomization for study intervention and assigned stratification by age

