**Table 4.1: Overall design**

Type of design	
Phase I/II, first-in-human, multi-center, safety and immunogenicity study comprised of 2 sequential cohorts:
 
 
Lead-in, open-label, Sentinel Cohort (initial target of 25 participants) with Complete Sentinel Early Safety Data Reviews (CS-ESDRs)
 
 
In case an alert threshold is met in a dose-level group, the Sentinel Cohort for the corresponding dose-level group could be expanded to reach a total of approximately 25 participants (Table 1.1).
 
 
Randomized, modified double-blind, placebo-controlled Full Enrollment Cohort (initial target of 308 participants, but actual number could be lower as it will be determined by dose-levels progressing after CS-ESDR). Includes Cohort 1 and Cohort 2 (Table 1.2).
 

Phase	I/II
Control method	
 
Open-label, without placebo group for Sentinel Cohort
 
Placebo-controlled for Full Enrollment Cohort
 

Study population	Healthy, adults 18 years of age and older without prior serologic evidence of SARS-CoV-2 infection
Level and method of blinding	
For Sentinel Cohort
 
 
Open-label without blinding of participants, site Investigators and staff, and Sponsor
 
No blinding for injection schedule as all participants will receive 2 vaccinations
 
 
For Full Enrollment Cohort
 
 
Blinding for vaccine group assignment (formulation): participants, outcome assessors, Investigators, laboratory personnel, Sponsor study staff
 
No blinding for injection schedule
 

	
 
Only study site staff who prepare and administer the vaccine and are not involved with the safety evaluations will be unblinded to study intervention assignment
 

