Clinical and epidemiological data also indicate that advanced age and those with chronic medical conditions are at increased risk of severe outcomes associated with COVID-19. The excess mortality from COVID-19 illness in the elderly may also be compounded by the higher prevalence of comorbidities in this age group (31) (32). Exclusion of individuals with chronic medical conditions from this study mitigates the potential risk of exacerbating poor outcomes as a result of study participation. The exclusion of individuals with chronic underlying conditions is also considered a risk mitigation measure to address the theoretical phenomenon of immune enhancement in this study population (17).

Another risk mitigation strategy is to restrict enrollment for the Sentinel Cohort to younger adults 18 through 49 years of age. After performing CS-ESDR-1 and if no safety signals or major tolerability concerns are identified in this cohort of younger participants, full enrollment will be opened to all younger and older age groups simultaneously. The simultaneous enrollment based on the inclusion of healthy older adults, at higher risk for severe outcomes and without evidence of previous SARS-CoV-2 infection is warranted and will prevent a delay in the program and allow rapid data generation to support further clinical development.

No upper age range is specified as long as other inclusion/exclusion criteria are met. Complete exclusion of older individuals from the study would compromise the timely progression of the clinical development plan and the deployment of the vaccine to the field (if a sequential enrollment of older adults was required), or result in selection of a formulation without knowledge about immunogenicity and safety patterns in older adults (if program progression was only informed by data from younger adults).

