5.1.1.4 Statistical Methods for Primary Immunogenicity Objective

The primary endpoints for the evaluation of immunogenicity are based on pseudovirus neutralizing antibody titers against D614 variant, which will be measured with the pseudovirus neutralization assay. The statistical analyses will be performed for the following primary endpoints below in each age and intervention group:

1. Neutralizing antibody titer on D01, D22, and D36
2. Fold-rise (fold-rise in serum antibody neutralization titer post-vaccination relative to D01) at D22, and D36
3. 2-fold and 4-fold rise in serum neutralization titer relative to D01 at D22, and D36
4. Occurrence of neutralizing antibody seroconversion, defined as baseline values below LLOQ with detectable neutralization titer above assay LLOQ at D22 and D36

The 95% CIs for the geometric mean titers (GMTs)/geometric mean concentrations (GMCs) and GMT ratios will be calculated using normal approximation of log-transformed titers. The 95% CIs for the proportions will be based on the Clopper-Pearson method. Additional parameters may be displayed as appropriate.

For descriptive purposes, the statistics presented in [Table 5.1](#) will be produced for each intervention group and each age group. The same dose-level group in Sentinel Cohort and Cohort 2 will be pooled for analysis.

Additionally, to evaluate independent determinants of primary immunogenicity endpoints, regression models may be constructed for log transformed titers and occurrence of 4-fold rise in serum neutralization titer relative to D01 at D22 for Cohort 1 and D36 for Sentinel Cohort and Cohort 2. When the outcome/dependent variable is a continuous numerical variable, linear model may be utilized; when the outcome/dependent variable is a categorical variable, logistic regression models may be utilized. Explanatory/independent variables inserted in these models would include age group (18-49 years, ≥ 50 years) and the injection schedule (1-injection, 2-injections). Models evaluating antibody titers or rates may include also an explanatory variable corresponding to the antigen dose level (ultra-low-dose, low-dose, medium-dose) when more than 1 dose level is to be used for the Full enrollment Cohort. Multiplicative interaction terms will be included in expanded models to assess for evidence of effect modification. Non-significant interaction terms with critical value < 0.05 can be removed from the models.

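### Immunogenicity is planned only with the non-randomized Sentinel participants pooled into the two-injection vaccine groups, so the 18-49 and all-ages two-injection results have no randomized-only view

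*SAP*

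**What the plan says.** SAP 5.1 treats safety and immunogenicity differently. Safety has two populations: "participants in the Full Enrollment Cohort (Cohort 1 and 2) only", and, if necessary, that cohort together with Sentinel. Immunogenicity and efficacy are to be "conducted based on the combined population (Full Enrollment Cohort + Sentinel Cohort) only". SAP 5.1.1.4 states which groups are merged: "The same dose-level group in Sentinel Cohort and Cohort 2 will be pooled for analysis". Since Cohort 2 is the two-injection cohort, Sentinel participants enter only the two-injection vaccine groups.

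The protocol describes Sentinel as a different kind of cohort:

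- Assignment (Synopsis, Overall Design): "Sentinel Cohort: sequentially assigned study intervention".
- Control (Table 4.1): "Open-label, without placebo group for Sentinel Cohort".
- Age (Section 4.2, Rationale for Study Population): the plan is to "restrict enrollment for the Sentinel Cohort to younger adults 18 through 49 years of age".

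The SAP also provides age-specific results. Section 5.1 says "Subgroup analyses will be performed by age-group", and Section 5.1.1.4 covers the "primary endpoints below in each age and intervention group". The regression models in 5.1.1.4 are optional. They include age group and injection schedule, may include dose, and have no term for Sentinel versus randomized cohort. SAP 5.7 drops the between-group GMT ratios and seroconversion differences, and also the complementary and sensitivity analyses of immunogenicity.

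**The concern.** Protocol 4.2 says that comparing Cohort 1 with Cohort 2 informs the choice of schedule, that comparing dose levels informs the choice of dose, and that the placebo arm supports unbiased evaluation of immunogenicity. The final report will show GMTs, confidence intervals and reverse cumulative distribution curves for each group, and readers will compare them.

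In these displays the two-injection vaccine groups contain people who were not randomized, were enrolled earlier, knew what they received and are all under 50. Placebo and Cohort 1 contain none of them. Splitting by age removes the difference in age mix. It does not show which of the younger two-injection recipients were randomized, and with the sensitivity analyses dropped, nothing else in the SAP does.

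**Working it through.** **Inputs.** Protocol Table 4.3: each Full Enrollment vaccine group has 20 participants aged 18-49 and 24 aged 50 or over (44); each placebo group has 10 and 12 (22). Protocol Table 4.2: Initial Sentinel has 10, 5 and 10 at the ultra-low, low and medium dose, each expandable to 25. Protocol 6.3.1: the low-dose expansion (20 more) has already been exercised. So s, the number of Sentinel participants per dose group, is 25 for the low dose and 10 for the other two, or 25 if those are expanded.

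**The plan's own figures.** Protocol 4.2 gives about 145 younger and 144 older vaccine recipients: 6 × 20 + 25 = 145 and 6 × 24 = 144. Protocol 9.2 gives 333 and a maximum of 383: 2 × (3 × 44 + 22) = 308; 308 + 25 = 333; 308 + 75 = 383. All agree.

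**Composition of a pooled two-injection vaccine group.**

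| Quantity | Formula | s = 0 | s = 10 | s = 25 |
|---|---|---|---|---|
| Share aged 18-49 | (20 + s)/(44 + s) | 20/44 = 45.5% | 30/54 = 55.6% | 45/69 = 65.2% |
| Excess over placebo and Cohort 1 | difference | 0 | 10.1 points | 19.8 points |
| Sentinel share, all ages | s/(44 + s) | 0% | 10/54 = 18.5% | 25/69 = 36.2% |
| Sentinel share, 18-49 | s/(20 + s) | 0% | 10/30 = 33.3% | 25/45 = 55.6% |
| Sentinel share, 50 or over | 0/24 | 0% | 0% | 0% |

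Placebo has 10/22 = 45.5% aged 18-49, as in Cohort 1. If only the low dose is expanded, the pooled dose groups also differ from each other by 65.2 − 55.6 = 9.6 points.

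**Effect of age mix on the all-ages GMT.** The log GMT is the mean of the log titres. If the younger-to-older GMT ratio is k, raising the younger share from p0 to p1 multiplies the all-ages GMT by k^(p1 − p0). The documents give no k, so a range is shown. Sentinel titres are assumed equal to those of randomized younger adults.

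| k (assumed) | s = 10 | s = 25 |
|---|---|---|
| 1.25 | 1.02 | 1.05 |
| 1.5 | 1.04 | 1.08 |
| 2 | 1.07 | 1.15 |
| 3 | 1.12 | 1.24 |

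**Early stop.** SAP 5.7 reports that enrollment ended early, but actual group sizes are not given. If half of the planned Full Enrollment number was reached (assumption), the younger share would be (10 + 10)/(22 + 10) = 62.5% for s = 10 and (10 + 25)/(22 + 25) = 74.5% for s = 25.

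**Analysis-set wording.** SAP 5.2.5 uses the mFAS for immunogenicity. The mFAS is a subset of the FAS (SAP 5.2.4), and SAP 5.2.1 limits the FAS to randomized participants. Read literally, that excludes the sequentially assigned Sentinel Cohort that SAP 5.1 pools. Protocol 9.3 builds the FAS from enrolled participants, and SAP 5.7 describes the mFAS as already used for the Sentinel interim analysis. Inclusion is evidently intended, but the definition does not say so.

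**The case against.** The strongest reply is that most of the apparent harm is already dealt with. Age-specific results are planned, so the age imbalance touches only the all-ages rows. A reader might infer that the regression schedule term is distorted by age; it is not, because age group and schedule stand in the same model. A reader might also infer that the randomized comparison is lost altogether. The documents do not support that: no Sentinel participant is 50 or over, and under the pooling rule in SAP 5.1.1.4 Cohort 1 and its placebo receive no Sentinel participants at any age. All of this stands.

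It can also be said that immunogenicity is descriptive, that the formal between-group contrasts were dropped, and that development has ended, so no dose or schedule decision depends on these tables. Protocol 4.2 foresaw that Sentinel would add to the younger-adult data. The Sentinel dosing errors are addressed by analysing as received, and open-label administration matters less for a laboratory titre than for a reported symptom. The GMT shift is modest beside sampling error: with an assumed log10 SD of 0.4 to 0.5, the 95% confidence limits of a GMT at n = 54 to 69 lie a factor of about 1.25 to 1.37 either side. These arguments lower the priority. They do not supply the missing view, and they give no reason why safety should have a Full-Enrollment-only analysis and immunogenicity should not.

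**Conclusion.** The concern holds in a limited form. In the 18-49 and all-ages two-injection vaccine results, randomized and sequentially assigned participants are merged and cannot be separated from the tables that the SAP describes. As planned, a third to just over half of the 18-49 part is Sentinel. Any regression schedule term is adjusted for age but not for cohort, so it also carries differences in enrollment period and open-label status.

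The age effect is confined to the all-ages rows: 10 to 20 points more younger adults and, under the assumed ratios, a GMT about 2% to 24% higher. The direction and size of that shift are assumptions, and the shares rest on planned numbers. The stratum aged 50 or over and Cohort 1 versus its placebo are unaffected, and no formal test or interval for a between-group contrast is biased, because none is planned. The reading that Sentinel joins only Cohort 2 rests on SAP 5.1.1.4; SAP 5.1 alone names the Full Enrollment Cohort. The separate tables, listings and figures document to which SAP 5.7 refers was not available. This is a worthwhile, inexpensive improvement to a descriptive report.

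**What to change.** 1. Add Full-Enrollment-only immunogenicity tables, overall and by age group, mirroring what SAP 5.1 provides for safety. Name them as the tables for reading schedule and placebo differences.
2. Keep the pooled tables as planned, with a footnote giving the number of Sentinel participants in each pooled group.
3. Add a Sentinel-versus-randomized term to any regression that is fitted.
4. Reword the FAS in SAP 5.2.1 (and so the mFAS) so that it states explicitly whether Sentinel participants are included, consistent with SAP 5.1 and Protocol 9.3.

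The cost is one more run of existing programs and a few lines of SAP text. The drawback is smaller groups in the Full-Enrollment-only view: 44 planned per vaccine group instead of 54 to 69, and fewer if enrollment fell short.
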